1.1 Scientific abstract

The overarching goals of our study are to (i) assess whether postpartum administration of a loop-diuretic reduces blood pressure prior to discharge in women at high risk for de novo postpartum hypertension; (ii) evaluate whether this reduction in blood pressure reduces the need for initiation of therapies to treat severe de novo postpartum hypertension; and (iii) evaluate whether this reduces the risk of hypertension-associated morbidity in the postpartum period.

Hypertensive disorders of pregnancy are one of the leading causes of maternal morbidity and mortality worldwide.^{1,2} The majority of clinical research has focused on pregnancy-related hypertension that develops in the antenatal period, while studies of the incidence, risk factors, and prevention of postpartum hypertension are limited. In particular, there is a paucity of data about the clinical entity known as de novo postpartum hypertension, in which women who are normotensive throughout pregnancy and delivery subsequently go on to develop high blood pressure in the immediate to late postpartum period. Of those with postpartum preeclampsia, 33-69% were normotensive antepartum.³⁻⁷

Early identification and treatment of antepartum preeclampsia has been shown to decrease some severe maternal outcomes. Conversely, women with de novo postpartum hypertensive disorders remain among the highest risk for severe maternal morbidity due to decreased surveillance and lack of data regarding identifiable and modifiable risk factors to facilitate stratification of monitoring, preventive therapies and intervention.⁸ Of women admitted with postpartum hypertensive complications, for example, two retrospective series estimate rates of eclampsia up to 78% in women with no antenatal diagnosis of hypertensive disorders of pregnancy, compared to rates ranging from 4.6% to 13.6% in women with antepartum or intrapartum diagnoses of hypertensive disorders.^{3,9}

Over the past two decades, multiple randomized controlled trials have demonstrated a benefit in the use of oral loop-diuretics in decreasing postpartum systolic blood pressure, promoting faster normalization of blood pressure and decreasing the need for antihypertensive therapy in women with an antenatal diagnosis of preeclampsia.¹⁰⁻¹² Given the implication of the normal physiologic auto-infusion of sequestered extravascular fluid into the intravascular space in the pathogenesis of hypertensive disorders in the postpartum period, we propose that this same therapy may have benefits in reducing hypertensive episodes and need for therapy in other women at high risk for postpartum hypertensive complications – specifically de novo postpartum

hypertension. In a randomized placebo-controlled trial design, we propose to use an oral loop diuretic (i.e. furosemide) to evaluate whether we can help prevent de novo postpartum hypertension by reducing blood pressure after delivery in high-risk women. We hypothesize that postpartum administration of the loop diuretic furosemide in women at high risk of developing de novo postpartum hypertension will reduce blood pressure at the time of discharge compared to placebo. The primary outcome of arterial blood pressure (MAP) will be compared between the study groups using student's t-test. Ultimately, we hypothesize that this will reduce the need for therapies to treat severe postpartum hypertension and will reduce hypertension-associated morbidity in the postpartum period. For analysis of categorical data in independent samples, the Chi-squared test or Fisher exact probability test will be utilized. Continuous data that satisfy the assumptions of normality and homoscedasticity (homogeneity of variance) will be analyzed by t-test.

1.2 Lay abstract

New-onset high blood pressure related to pregnancy is one of the leading causes of maternal complications and death worldwide.^{1,2} Most of what is known about pregnancy-related high blood pressure comes from studies of women who develop high blood pressure while they are still pregnant. There is little data that exists about the clinical entity known as “de novo postpartum hypertension”, in which women who have normal blood pressure throughout pregnancy and delivery subsequently go on to develop high blood pressure within two days to six weeks after giving birth, also known as the postpartum period. Of all the women who develop high blood pressure in the postpartum period, one third to two thirds of them had normal blood pressure during pregnancy.³⁻⁷

Early identification and treatment of the complications of pregnancy-related high blood pressure while women are still pregnant have been shown to decrease some severe maternal outcomes, such as seizures (i.e. eclampsia), strokes, and death. On the other hand, women with de novo postpartum hypertension remain among the highest risk for severe maternal complications, such as eclampsia.⁸ This occurs because there is a lack of data to identify who is at high risk for de novo postpartum hypertension and may need continued close follow up after delivery and what preventive measures or treatments can be provided to reduce the risk of complications. Studies of women admitted to the hospital after delivery for high blood pressure-related complications estimate that the rates of eclampsia were as high as 78% in women who had normal blood pressure during pregnancy compared to rates ranging from 4.6% to 13.6% in women who were diagnosed with high blood pressure during pregnancy or labor and delivery.

Over the past two decades, high quality data has shown that for women diagnosed with preeclampsia during pregnancy, giving them a medication known as a loop diuretic after they deliver reduces their blood pressure, helps their blood pressure to return to normal faster, and reduces their need for high blood pressure medication.¹⁰⁻¹² This same therapy may have similar benefits in women at high risk for new-onset high blood pressure after they give birth, and may ultimately reduce their risk of severe complications, such as seizures and strokes.

2. Proposal body

2.1 Background

Hypertensive disorders of pregnancy are one of the leading causes of maternal morbidity and mortality worldwide.^{1,2} The majority of clinical research has focused on pregnancy-related hypertension that develops in the antenatal period, while studies of the incidence, risk factors, and prevention of postpartum hypertension are limited. In particular, there is a paucity of data about the clinical entity known as de novo postpartum hypertension, in which women who are normotensive throughout pregnancy and delivery subsequently go on to develop high blood pressure in the immediate to late postpartum period. Of those with postpartum preeclampsia, 33–69% were normotensive antepartum.³⁻⁷

Early identification and treatment of antepartum preeclampsia has been shown to decrease some severe maternal outcomes. Conversely, women with de novo postpartum hypertensive disorders remain among the highest risk for severe maternal morbidity due to decreased surveillance and lack of data regarding identifiable and modifiable risk factors to facilitate stratification of monitoring, preventive therapies and intervention.⁸ Of women admitted with postpartum hypertensive complications, for example, two retrospective series estimate rates of eclampsia up to 78% in women with no antenatal diagnosis of hypertensive disorders of pregnancy, compared to rates ranging from 4.6% to 13.6% in women with antepartum or intrapartum diagnoses of hypertensive disorders.^{3,9}

Over the past two decades, multiple randomized controlled trials have demonstrated a benefit in the use of oral loop-diuretics in decreasing postpartum systolic blood pressure, promoting faster normalization of blood pressure and decreasing the need for antihypertensive therapy in women with an antenatal diagnosis of preeclampsia.¹⁰⁻¹² The rationale for its efficacy is the implication of the normal physiologic auto-infusion of sequestered extravascular fluid into the intravascular space in the pathogenesis of hypertensive disorders in the postpartum period. Given that this same mechanism may play a role in the pathogenesis of postpartum hypertension, **we propose that this same therapy may have benefits in reducing hypertensive episodes and need for therapy in other women at high risk for postpartum hypertensive complications – specifically de novo postpartum hypertension. Therefore, the purpose of this study is to evaluate whether furosemide can help prevent de novo postpartum hypertension by reducing blood pressure after delivery in high-risk women.**

2.2 Specific aims

Our objective is to trial furosemide in women at high risk for developing de novo postpartum hypertension in a randomized control design, with an aim to reduce blood pressure at the time of discharge from the delivery hospitalization and thereby reduce the frequency of postpartum hypertensive episodes requiring therapy and reduce severe morbidity and mortality.

Specific Aim 1. To compare the mean blood pressures over the 24 hours prior to discharge or prior to antihypertensive therapy initiation (whichever occurs first) in women who have been randomized to a 5-day course of PO furosemide 20 mg daily (study drug) to those who have been randomized to a 5-day course of PO placebo daily (placebo). We hypothesize that women taking PO furosemide 20 mg daily will have lower mean blood pressure in the 24 hours

prior to discharge or prior to antihypertensive therapy initiation compared with patients taking placebo.

- **Sub-aim 1: To compare the rates of diagnosis of postpartum hypertension and preeclampsia between those who have been randomized to the study drug and those randomized to placebo from the time of delivery to 6 weeks postpartum.** We hypothesize that women randomized to the study drug will have lower rates of postpartum hypertension and preeclampsia.
- **Sub-aim 2: To compare percentage of elevated blood pressures postpartum between those who have been randomized to the study drug to those randomized to placebo from the time of delivery to 6 weeks postpartum.** We hypothesize that women randomized to the study drug will have fewer hypertensive episodes.
- **Sub-aim 3: To compare the frequency of postpartum hypertension-related triage and emergency department visits between those who have been randomized to the study drug to those randomized to placebo from the time of discharge to 6 weeks postpartum.** We hypothesize that women randomized to the study drug will have fewer triage and emergency department visits for hypertension-related complaints episodes after discharge.
- **Sub-aim 4: To analyze factors associated with response to therapy.** We hypothesize that factors such as degree of lower extremity edema and indication for high risk status will be associated with greater response to therapy.

Specific Aim 2. To compare rates of initiation of hypertensive therapies in women randomized to the study drug compared to those randomized to placebo. We hypothesize that women randomized to the study drug will be less likely to be initiated on hypertensive therapies between delivery and 6 weeks postpartum.

Specific Aim 3. To compare rates of severe maternal morbidity in women randomized to the study drug compared to those randomized to placebo from the time of discharge to 6 weeks postpartum. We hypothesize that women randomized to the study drug will have lower rates of severe maternal morbidity between delivery and 6 weeks postpartum compared to those randomized to placebo.

- **Sub-aim 1: To compare hypertensive-related unscheduled presentations between those who have been randomized to the study drug and those randomized to placebo.** We hypothesize that women randomized to the study drug will have fewer triage and emergency department visits for hypertension-related complaints episodes after discharge.
- **Sub-aim 2: To assess adverse effects of therapy in the study group and the control group.** We hypothesize that there will be no difference in adverse effects, such as discontinuation of breastfeeding, hypotension, and electrolyte abnormalities in women randomized to the study drug compared to those randomized to placebo.
- **Sub-aim 3: To analyze factors associated with incidence of severe maternal morbidity in the study group and the control group.** We hypothesize that factors such as racial and ethnic identity and age will be associated with increased incidence of severe maternal morbidity.

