Patient written informed consent and HIPAA authorization to participate in the study will be collected on an iPad or laptop. In-person electronic signature will be captured on the electronic informed consent form. Study personnel obtaining consent will be physically present at time of signature. A paper copy of the signed informed consent form will be given to the patient. A copy of the signed consent form will also be placed in the patient's inpatient paper chart. The time of consent will be documented on the consent form and in the medical record.

Consent forms will be available in both English and Spanish to accommodate our expected population. A witness will be required for our non-English speaking patients.

At the time of the consent, the Informed Consent Process will begin with a concise and focused presentation of the key information about the research study. The collaborating investigators will explain the study, and potential subjects will have an opportunity to discuss the information provided. The collaborating investigators will answer any questions. The Informed Consent Process as a whole presents information in sufficient detail relating to the research study. Consent will be obtained to measure blood pressures postpartum. Consent will be obtained to review medical records to abstract pertinent sociodemographic and clinical information and to call patients to obtain the aforementioned information if not able to be abstracted from the medical record. Consent will be obtained to administer electronic surveys and collect home blood pressure measurements at two postpartum study visits. Patients still meeting inclusion criteria will be randomized at within eight hours of delivery on the postpartum service.

Enrollment

After obtaining written informed consent, participants will be randomized to either the study drug, as defined above, or placebo. Randomization will occur through the Columbia Research Pharmacy in REDCap. The medication intervention will be dispensed to the patient's postpartum unit and administered by the nursing staff once daily beginning within eight hours of delivery. The patient, the patient's nurse, and the patient's inpatient obstetric provider will not be informed

of the patient's randomization group, to avoid potential biases stemming from differences in inpatient care. Participants will be enrolled in the study from the time of randomization until 6 weeks postpartum.

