2.3.6 Outcomes

- 1) **Primary outcome:** Our primary outcome will be the difference in mean arterial pressure (MAP) averaged over the 24 hours prior to discharge or the 24 hours prior to antihypertensive therapy initiation (whichever occurs first).
- 2) **Secondary outcomes:** Secondary outcomes will include:
 1. Rates of de novo postpartum preeclampsia – determined at discharge, at 2 and at 6 weeks postpartum
 2. Percentage of recorded blood pressure that are elevated (>140 systolic OR >90 diastolic) – calculated at the time of discharge, at 2 weeks, and at 6 weeks

3. Rates of magnesium sulfate administration – determined at discharge, at 2 and at 6 weeks postpartum
4. Time to discharge
5. Rates of initiation of antihypertensives – determined at discharge, at 2 and at 6 weeks postpartum
6. Rates of severe maternal morbidity (e.g. stroke, seizure, PRES) – determined at 6 weeks postpartum
7. Mean frequency of triage or ED presentation/readmission – determined at 2 and at 6 weeks postpartum
8. Breastfeeding continuation rates – determined at about 2 weeks and at 6 weeks postpartum
9. Neonatal outcomes

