2. **Adherence.** For both groups, proportion of medication course completed will be recorded
3. **Time to initiation of medications.** For both groups, time to initiation of anti-hypertensive medications will be tracked
4. **Final plan at 6 weeks.** For both groups, continuing medication regimens at 6 weeks will be collected.
5. **Hospital readmissions.** Hospital readmission for any indication will be collected for both groups
6. **Triage/ED visits.** Presentation to the obstetric triage unit or the emergency department for any indication will be collected for both groups
7. **Maternal morbidity and mortality.** Incidences of eclampsia, stroke, PRES, maternal death will be collected for both groups
8. **Breastfeeding continuation.** Rates of breastfeeding continuation will be collected for both groups
9. **Adverse effects.** Incidences of hypotension, electrolyte abnormalities, and development of renal insufficiency will be collected for both groups.

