De novo postpartum hypertensive disorders of pregnancy will be defined according to the aforementioned criteria and definitions, except for their timing of occurrence after delivery, and in the absence of any antenatal diagnosis of a hypertensive disorder of pregnancy.

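### Aim 3 starts the severe-morbidity comparison at discharge in its objective but at delivery in its hypothesis, and its expectation of equal harms has no effect estimate or interval to support it

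*Combined protocol and SAP*

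**What the plan says.** **Morbidity window.** The objective of Specific Aim 3 (section 2.2) compares severe maternal morbidity in women "randomized to the study drug compared to those randomized to placebo from the time of discharge to 6 weeks postpartum". The hypothesis that follows says that women given the study drug "will have lower rates of severe maternal morbidity between delivery and 6 weeks postpartum". The outcome list in section 2.3.6 gives an assessment time and no start: "Rates of severe maternal morbidity (e.g. stroke, seizure, PRES) – determined at 6 weeks postpartum". Aim 1, sub-aim 1, on new diagnoses of hypertension or preeclampsia, does start at delivery; its comparison is of "those who have been randomized to the study drug and those randomized to placebo from the time of delivery to 6 weeks postpartum". Section 2.3.8 gives de novo postpartum disorders the antenatal criteria, "except for their timing of occurrence after delivery", and eclampsia is among those criteria. Section 2.3.7 lists, among data gathered throughout the study: "Incidences of eclampsia, stroke, PRES, maternal death will be collected for both groups". On timing of randomisation, section 2.3.4 says: "Patients still meeting inclusion criteria will be randomized at within eight hours of delivery on the postpartum service".

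**Harms.** Aim 3, sub-aim 2 sets out to assess adverse effects and hypothesises that they will not differ between arms, naming stopping breastfeeding, hypotension and electrolyte abnormalities. Section 2.3.7 adds renal insufficiency. Section 2.5 anticipates benefit without harm, although section 2.10.1 notes that the drug may inhibit lactation. Section 2.4.2 gives Chi-squared or Fisher tests for categorical data, logistic regression where appropriate, and significance at p < 0.05 in all cases. It mentions no risk difference and no confidence interval.

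**The concern.** The two Aim 3 sentences define different sets of countable events. A woman who has an eclamptic seizure on the postpartum ward, after randomisation, has a de novo disorder under section 2.3.8 and counts under the hypothesis. Under the objective she does not count. Discharge is also a poor origin for a randomised comparison. It falls after randomisation, and "Time to discharge" is a listed secondary outcome, so the window could open at different times in the two arms if treatment affects length of stay. Severe events are likely to be few in 82 women, so the window should not be left for choice once the data are known.

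For harms, the hypothesis is one of similarity, but the only stated between-arm tool is a test of difference in a trial sized for blood pressure. A non-significant result would be likely even with a material excess of harm, and it could be taken as confirming the hypothesis.

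**Working it through.** **1. Does any section settle the start of the morbidity window?**

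| Section | What it fixes | Start of the comparison? |
|---|---|---|
| 2.2, Aim 3 objective | comparison window | discharge |
| 2.2, Aim 3 hypothesis | comparison window | delivery |
| 2.3.1 | follow-up, recruitment to 6 weeks | not stated |
| 2.3.4 | enrolment, randomisation to 6 weeks | not stated |
| 2.3.6 | assessment at 6 weeks | not stated |
| 2.3.7 | collection throughout the study | not stated |
| 2.10.4 | monitoring, 6 weeks from delivery | not stated |

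Collection covers the inpatient stay. Only the two Aim 3 sentences say which events enter the comparison, and they disagree.

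**2. How much time is at issue?** The documents give no length of stay. Assuming discharge 1 to 4 days after delivery, a discharge start removes 1/42 = 2.4% to 4/42 = 9.5% of the six weeks, and roughly 1/5 = 20% to 4/5 = 80% of the five-day course. These are shares of time, not of events. The documents give no stroke, seizure or PRES rate for this population, so no expected event count follows.

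**3. What the sample size was built for.** Section 2.4.1 uses a difference of 5 mm Hg, SD 6.4, 90% power, 5% significance (taken as two-sided) and 10% losses. The normal formula gives n = 2 × (1.960 + 1.282)² × (6.4/5)² = 34.4, so 35 per arm and 35/0.9 = 38.9, so 39. The t-based calculation gives 35.4, so 36 per arm and 36/0.9 = 40. The plan's 41 per arm is within one of the t-based figure. There is no sample-size error, but the calculation concerns MAP only. After the planned losses, 41 × 0.9 = 36.9, so about 37 per arm.

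**4. What 37 to 41 per arm can say about harms.** No harm rates are given, so the counts are illustrative. With Wilson limits l and u for each arm's proportion p, the Newcombe limits for the risk difference at equal counts are ±√[(p − l)² + (u − p)²].

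| Counts | n per arm | p (%) | Wilson l to u (%) | Newcombe 95% limits (points) |
|---|---|---|---|---|
| 2 vs 2 | 37 | 5.41 | 1.50 to 17.70 | ±√(3.91² + 12.29²) = ±12.9 |
| 2 vs 2 | 41 | 4.88 | 1.35 to 16.14 | ±√(3.53² + 11.26²) = ±11.8 |
| 8 vs 8 | 37 | 21.62 | 11.39 to 37.20 | ±√(10.23² + 15.58²) = ±18.6 |
| 8 vs 8 | 41 | 19.51 | 10.23 to 34.01 | ±√(9.28² + 14.50²) = ±17.2 |

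With no events at all in an arm, the exact upper limit 1 − 0.025^(1/n) is 9.5% for n = 37 and 8.6% for n = 41.

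**5. Power of the planned test.** At 37 per arm, assumed rates of 5% and 15% give 16% power by Fisher and about 30% by the Chi-squared approximation. A tripling from 5% would usually be non-significant.

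**The case against.** **On the window.** The discharge phrase is plausibly a slip. The same wording appears in Aim 1, sub-aim 3, on triage and emergency visits, where a discharge start makes sense. Everything operational (follow-up, enrolment, collection, monitoring) spans the inpatient stay. This stands to the extent that the fix is one phrase. It does not settle the conflict, because collecting an event and including it in a comparison are separate decisions. A reader might infer that inpatient events go unrecorded, or that the result will be biased. The documents support neither: the events are collected, and any difference in window start by arm depends on an effect on length of stay that is unknown.

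**On harms.** Section 2.4.2 is a generic list for every outcome, and nothing says that p ≥ 0.05 will be reported as equality. Sub-aim 2 says the aim is to assess; equality is a hypothesis. Sections 2.3.6 and 2.3.7 call for rates and incidences by group, logistic regression could yield an interval, and section 2.10.4 gives safety review to a DSMB and the investigators. All of this stands. It would be wrong to say that safety is judged by p-values alone; the gap is in the between-arm comparison, where no estimate or interval is specified.

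**On size.** A reader might infer that the plan could hide an excess above 25 points. That needs lopsided counts. For example, 7 vs 2 of 41 gives Fisher p = 0.155 with limits of −1.9 to 26.8, and a report of 17% vs 5% would hardly look like equality. When counts are close, the limits are nearer 12 to 19 points.

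**Conclusion.** Both parts hold in limited form. The start of the severe-morbidity comparison is contradictory within Aim 3 and is not resolved elsewhere. The discharge reading would leave out on-treatment inpatient events and start at a post-randomisation outcome. No data are lost, and the number of events affected cannot be estimated from the documents.

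The hypothesis that harms do not differ cannot be supported by a non-significant test with 37 to 41 women per arm: identical counts are still compatible with differences of about 12 to 19 points. That range rests on the illustrative counts of 2 and 8 per arm and on losses of 0 to 10%. The primary MAP analysis and the sample size are unaffected.

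A reader might also treat delivery and randomisation as interchangeable starts. They can be up to 8 hours apart, and an event in that gap precedes both allocation and study drug.

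**What to change.** **Window.** Change the Aim 3 objective to run from delivery to 6 weeks, matching its own hypothesis, and carry the same window into section 2.3.6. State that the between-arm comparison counts events from randomisation in all randomised women, and that any event between delivery and randomisation is listed separately.

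**Harms.** In section 2.4.2, for each of hypotension, electrolyte abnormalities, renal insufficiency and breastfeeding discontinuation, name as the result the events/n by arm and the risk difference with a 95% Newcombe interval. State that p ≥ 0.05 will not be read as no difference. No equivalence margin is needed.

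**Cost.** Wording only, with no extra participants or visits. The safety statements will be more modest. Fisher and Newcombe can disagree at the edge (5 vs 0 of 41: Fisher p = 0.055, interval 1.2 to 25.5 points), so the interval should be named in advance as the harm result.
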